8. DATA COLLECTION

Study data will be entered into an eCRF developed by Edinburgh Clinical Trials Unit. A source data plan will be created to indicate where the study data are originally documented. The study data obtained from electronic health records will either be entered directly into the eCRF or held in a trusted research environment. International sites will use their own data collection system to record the study data and the electronic health record data.

8.1 DATA MANAGEMENT

8.1.1 Personal Data

The following personal data will be collected as part of the research:

Participant's name, address, date of birth, GP contact details, health information and unique health identifier (Community Health Index (CHI) number or National Health Service (NHS) number will be collected. Personal data will be stored securely in the eCRF and by the research team at each site for a minimum of 5 years after the study has finished. The location and duration of storage of personal data at the international sites will be documented in their country specific protocol.

8.1.2 Transfer of Data

Data collected or generated by the study may be transferred to external individuals or organisations outside of the Sponsoring organisation(s). It may be provided to researchers running other research studies outwith NHS Lothian/University of Edinburgh. Following publication of the primary paper, a de-identified individual participant data set will be submitted to a data archive for sharing purposes. Participant information will only be used by organisations and researchers to conduct research in accordance with the UK Policy Framework for Health and Social Care Research. Where this information includes identifiable information, it will be held securely with strict arrangements about who can access the information.

In order to perform data linkage, participant's personal details including their unique health number will be transferred to central health care and government data services bodies.

8.1.3 Data Processor

The data processor is the Edinburgh Clinical Trials Unit, Usher Institute, University of Edinburgh.

8.1.4 Data Controller

The data controller is the University of Edinburgh and NHS Lothian who are the co-sponsors of this study.

9. STATISTICS AND DATA ANALYSIS

9.1 PROPOSED SAMPLE SIZE

We plan to recruit 18,318 patients over 3 years across all participating countries. Of these, based on contemporary practice data for Scotland just under 7.5% will be treated with either coronary artery bypass graft surgery or percutaneous coronary intervention with a bare metal stent, giving a minimum sample size (excluding this 7.5%) for the main analysis of 16,944. If there is no substantial heterogeneity in outcome between these two groups, then they can be included in the analysis and further increase the power.

Recruitment in the UK was halted after 4,576 patients because the funder felt the trial was no longer deliverable due to the current challenging environment. The

statistical analysis will include the 4,576 patients recruited in the UK and as many international patients who have completed follow-up at the time of analysis.

9.2 SAMPLE SIZE CALCULATION

No clinical trials have been published comparing duration of therapy for unselected patients with type 1 myocardial infarction. However, most patients with type 1 myocardial infarction now undergo early percutaneous coronary intervention. From meta-analysis of stent trials comparing ≤ 6 months with 12 months of dual antiplatelet therapy [Palmerini et al, 2015] (among whom a large proportion of patients had acute coronary syndrome), the point estimates of the hazard ratios for all-cause mortality, non-cardiac mortality and bleeding were 0.87, 0.83 and 0.58 respectively. Over a 5-year period (2006-2010) in Scotland 25.4% of patients died within one year of acute coronary syndrome of whom 7.6% died from a non-cardiovascular cause, and 0.92% had a fatal bleed.

The study has been powered to assess the primary endpoint of all-cause mortality across the combined medical therapy and percutaneous coronary intervention with drug-eluting stent arms (92.5% of the study population). Assuming a more conservative relative risk reduction of 10% (risk ratio 0.9), and that patients who consent to participate in the study have a one-third lower overall risk of mortality than unselected patients, shorter durations of therapy would lead to an absolute difference of 1.69% ($0.1 \times 0.254 \times 0.667$) from the 12-month duration of treatment rate of 16.9%. A sample size of 8,472 patients per group (16,944 overall) would provide 85% power to detect this difference at two-sided $P<0.05$ (Stata 15.1 procedure 'power two-prop' without continuity correction). Given that this is an outcome ascertained by record linkage for geographically highly stable populations, we anticipate close to zero loss to follow up. To achieve the 16,944 across combined medical therapy and percutaneous coronary intervention with drug-eluting stent arms (92.5% of the study population) we need to randomise $16,944/0.925 = 18,318$ participants. In addition, the study will have slightly increased power by using not just the occurrence of the event but also incorporating the time-to-event using log-rank statistics (and Cox proportional hazards models to adjust for baseline covariates).

An initial check of the data linkage procedures will be performed at approximately 10% of recruitment. The independent Trial Steering Committee will monitor all the assumptions behind the sample size calculations in aggregated data as the trial progresses. The full sample size of 16,944 would also allow us to detect an absolute risk reduction of 1% (from 6% to 5%) in non-cardiovascular mortality with 81% power and an absolute risk reduction of 0.3% (from 0.6% to 0.3%) in bleeding death, with 83% power and two-sided $P<0.05$, with event rates being one-third lower in consented than in unselected patients. We do not expect to have power to estimate the treatment effect in coronary artery bypass graft surgery or percutaneous coronary intervention with bare metal stent groups.

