1.7 SCIENTIFIC PRINCIPLES UNDERLYING THE PROPOSED RESEARCH

We propose a novel approach to assess the strategy for the duration of dual anti-platelet therapy in type 1 myocardial infarction using routinely collected electronic health records linked to an international randomised controlled trial [Ford & Norrie, 2016]. We will compare the proportion of patients with different baseline

characteristics (in terms of bleeding and atherothrombotic risks) among those included and not included in the trial (those who are not approached or refuse to participate) and within countries, where possible.. This design (i) facilitates a large adequately powered trial, (ii) represents 'real world' clinical practice and includes all patients who, in the opinion of the treating physician, should be managed with dual anti-platelet therapy, (iii) will allow valid extrapolation of results to patients who would otherwise not participate in clinical trials and who arguably have the greatest potential to incur benefits and risks, (iv) makes for a highly efficient and cost-effective method of research delivery, (v) ensures optimal comparability and avoidance of bias, and (vi) generates adequate statistical power to address these pressing clinical questions.

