2. STUDY OBJECTIVES

Our principal question is: should the default strategy for the duration of dual anti-platelet therapy be 3 or 12 months after type 1 myocardial infarction? Given the opposing long-term harms and short-term benefits of dual antiplatelet therapy from recent meta-analyses, we propose to focus on the primary end-point of all-cause mortality. All-cause mortality is felt to be the only single outcome which could reliably capture the trade off in benefit from avoiding recurrent cardiovascular events in the acute term (part of which benefit should lead to fewer deaths) and the harms from bleeding over the longer term (part of which will lead to more deaths). All-cause mortality is also a simple outcome to measure and is highly complete and accurate in routine datasets, and any difference or similarity seen in all-cause mortality should be convincing as to which is overall the better duration of therapy for both patients and clinicians.

Of course, secondary outcomes such as cardiovascular death, myocardial infarction, non-cardiovascular death and major bleeding will also be of major interest. We may also be able to identify subgroups of patients who experience substantially greater benefits or on the other hand have much greater hazards, which will allow a more nuanced recommendation for a treatment policy than simply one size fits all.

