11 TRIAL MANAGEMENT AND OVERSIGHT ARRANGEMENTS

11.1 TRIAL MANAGEMENT GROUP

The trial will be managed and run by the Edinburgh Clinical Trials Unit which has full registration with the United Kingdom Clinical Research Collaboration. The study will be managed by a dedicated trial manager with support from a data programmer. The Clinical Trials Unit will also oversee the statistical and analytic aspects of the trial conduct.

11.2 TRIAL STEERING COMMITTEE.

The Trial Steering Committee (TSC) will be composed of external independent clinical trialists. They will oversee and support the strategic delivery of the trial by working with the applicants and Trial Management Group to deliver the goals of this innovative and challenging study. The terms of reference of the Trial Steering Committee, and the names and contact details are detailed in the TSC charter.

11.3 DATA MONITORING COMMITTEE.

The Data Monitoring Committee (DMC) will be composed of external independent experts. They will review emerging trial data to ensure the safety of patients and the integrity of the trial data as it emerges during study conduct. Interim analyses of the follow-up data will be supplied at approximately 25%, 50%, 75% and 100% mature data on the primary outcome (all-cause mortality) to ensure there is no overwhelming evidence of safety or efficacy that would require early termination of the trial. Appropriate criteria cannot be specified precisely, but the DMC will work on the principle that a difference of at least 3 standard errors in an interim analysis of a major outcome event (e.g. the primary outcome) may be needed to justify halting, or modifying, a study before the planned completed recruitment or trial follow-up. The terms of reference of the Data Monitoring Committee and the names and contact details are detailed in the DMC charter.

Due to recruitment being halted by the funder the first interim analysis at approximately 25% mature data on the primary outcome will coincide with final reporting.

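### The 85%, 81% and 83% power figures hold for 16,944 patients; neither document restates power or precision for the 4,576 UK patients plus an unstated international number that will be analysed

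*Protocol*

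**What the plan says.** Protocol 9.2 powers the trial on all-cause mortality: 16.9% at one year with 12 months of therapy, a risk ratio of 0.9, two-sided 5%, two proportions, no continuity correction. It states that "A sample size of 8,472 patients per group (16,944 overall) would provide 85% power to detect this difference". For the same 16,944 it claims to "detect an absolute risk reduction of 1% (from 6% to 5%) in non-cardiovascular mortality with 81% power", and 83% power for bleeding death (0.6% to 0.3%), "with event rates being one-third lower in consented than in unselected patients". The unselected rates come from the Scottish data quoted earlier in 9.2: 25.4% died within a year, "of whom 7.6% died from a non-cardiovascular cause, and 0.92% had a fatal bleed".

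Protocol 9.1 reports that "Recruitment in the UK was halted after 4,576 patients" and that international patients with completed follow-up will be added, without a number. Section 9.3 promises methods that allow for early stopping and few events. Section 11.3 says that "the first interim analysis at approximately 25% mature data on the primary outcome will coincide with final reporting".

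Three full-size statements remain without qualification. Section 1.7 says the design "generates adequate statistical power to address these pressing clinical questions". Section 2 says that "any difference or similarity seen in all-cause mortality should be convincing as to which is overall the better duration of therapy". SAP section 1 still gives the aim of 18,318.

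The SAP (V2.0, June 2025) has no sample-size or power section. SAP 4.5 reports the primary result as an adjusted hazard ratio with 95% CI and p-value, plus restricted mean survival and a 15-month absolute difference. SAP 4.6 tells readers to focus on effect size and CI for secondary outcomes; SAP 4.5 has no matching sentence for the primary.

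**The concern.** The only primary-outcome power figure in either document is 85%, and it belongs to a sample that will not exist. A reader who sets it beside the section 2 sentence could take a hazard ratio close to 1 as good evidence that 3 and 12 months are alike. In the reduced sample such a result may be fully compatible with the 10% reduction the trial was designed to detect.

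The SAP adapts other parts of the plan to the smaller sample: footnote 1 keeps the small bypass and bare-metal-stent groups in the analysis, and footnote 3 drops centre from the main model. The statement of what the sample can show was not updated in the same way.

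A smaller point sits in the same section. The 6% non-cardiovascular death rate does not follow from the one-third reduction that its own sentence applies.

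**Working it through.** **Inputs (Protocol 9.2 unless noted).** p1 = 0.254 × 0.667 = 0.1694; p2 = 0.9 × p1 = 0.1525; 1:1 allocation; two-sided 5%. UK number 4,576, or 2,288 per arm (9.1). Follow-up 15 months from index infarction (SAP 4.5). The international number is not given, so totals of 5,000 to 8,000 are an assumption.

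**Formula.** Power = Φ{[|p1 − p2| − 1.96√(2p̄(1 − p̄)/n)] / √[(p1(1 − p1) + p2(1 − p2))/n]}, with n per arm and p̄ the mean of p1 and p2.

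**Step 1: reproduce the plan.** n = 8,472: (0.01694 − 1.96 × 0.005646)/0.005645 = 1.04, so power is 85.1%. The same formula gives 81.5% for 6% v 5% and 83.1% for 0.6% v 0.3%. And 16,944/0.925 = 18,318. All agree with the protocol.

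**Step 2: UK patients alone.** n = 2,288: (0.01694 − 1.96 × 0.010865)/0.010862 = −0.40, so power is 34.4%. The secondary lines become 31.7% and 32.9%. A log-rank (Schoenfeld) check on about 736 deaths gives 35% for mortality.

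**Step 3: vary the total (one-year rates).**

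| Total analysed | All-cause death | 6% v 5% | 0.6% v 0.3% |
|---|---|---|---|
| 16,944 | 85% | 81% | 83% |
| 4,576 (UK) | 34% | 32% | 33% |
| 5,000 (assumed) | 37% | 34% | 35% |
| 6,000 (assumed) | 43% | 40% | 41% |
| 8,000 (assumed) | 54% | 50% | 52% |

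SAP 4.1 and footnote 2 of SAP 4.5 exclude reclassified and withdrawn patients. If that removed 5% to 10% of UK patients (assumption), UK-only primary power would be 33% to 32%.

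**Step 4: vary follow-up and mortality.** Constant hazard to 15 months: 1 − (1 − 0.1694)^1.25 = 20.7% and 1 − (1 − 0.1525)^1.25 = 18.7%. Power is 40.7% at 4,576 and 62.5% at 8,000. Given the one-year rates, this is an upper bound, because the protocol's Introduction says event rates fall after three months. In the other direction, at the 5.4% trial-average mortality in Protocol Table 2, power is about 13% at 4,576 and 19% at 8,000.

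**Step 5: precision.** CI factor = exp(1.96 × 2/√deaths).

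- 4,576 × 0.161 = 737 deaths: factor 1.155. An observed HR of 1.0 has a CI of 0.87 to 1.16. The lower limit passes 0.90 once the observed HR exceeds 0.90 × 1.155 = 1.04.
- 4,576 × 0.197 = about 900 deaths (15 months, constant hazard): factor 1.14, CI 0.88 to 1.14; 0.90 is excluded above about 1.03.
- For a CI centred on 1.0 to exclude 0.90: (2 × 1.96/ln(1/0.9))² = 1,384 deaths. That is about 8,600 patients at one-year mortality (1,384/0.161) or about 7,030 at the 15-month extrapolation (1,384/0.197).

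**Step 6: the 6% rate.** 25.4% × 2/3 = 16.9% and 0.92% × 2/3 = 0.61% follow the rule; 7.6% × 2/3 = 5.07%, not 6%. At 8,472 per arm, a 1-point fall from 5.07% has 87.7% power. Keeping the ratio instead gives 76% at 0.83 (the non-cardiac mortality hazard ratio quoted in 9.2) or 74% at 5/6 (the ratio in 6% to 5%).

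**The case against.** The strongest reply is that nothing is hidden and nothing is miscalculated. The 85% is tied to 16,944 in its own sentence, the next paragraph refers to the full sample size, and 9.1 reports the halt immediately before 9.2. Section 11.3 puts maturity at about 25%, and 4,576/18,318 is 25.0%. All of this stands. A reader might infer that the protocol misstates its power or conceals the shortfall; the documents do not support that. The fault is an omission.

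Second, sections 1.7 and 2 describe the merits of the design and justify the choice of endpoint. They are not interpretation rules, and no equivalence or non-inferiority conclusion is planned. This is also fair. But section 2 does speak of similarity as convincing, and nothing in SAP 4.5 says otherwise.

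Third, one might infer that any non-significant result would leave the 10% reduction open. That goes too far: with 737 deaths, a non-significant hazard ratio between about 1.04 and 1.155 would exclude 0.90. With enough international patients the problem near 1.0 could also disappear: at 8,000 patients and the 15-month extrapolation, a CI centred on 1.0 would be about 0.91 to 1.10.

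Fourth, recruitment is over, so restated power changes no design decision. True, but expected precision still governs how the result is read.

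On the minor point, it is tempting to call the 81% conservative. That holds only if the 1-point difference is kept; if the ratio is kept, power falls below 81%.

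**Conclusion.** The point holds as a gap in reporting and interpretation. The three powers are right for 16,944, and the documents give none for the sample to be analysed. On the protocol's own one-year rates, UK patients alone have about 34% power for all-cause mortality, and at most about 41% at 15 months. Assumed totals of 5,000 to 8,000 have 37% to 54% at one-year rates. Lower mortality than planned would reduce all of these.

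At the UK number, an observed hazard ratio near 1.0 would not exclude the planned 0.90, so it could not support the section 2 reading of similarity. This is limited to estimates near or below 1.0 and to totals short of roughly 7,000 to 8,600, depending on the follow-up and mortality assumed.

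The 6% rate is a genuine internal contradiction, but the sample size does not rest on it and the direction of its effect on power depends on which effect measure is held fixed. The main point should be corrected before results are reported; the 6% is minor.

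**What to change.** 1. Protocol 9.2: label 85%, 81% and 83% as figures for the original target. Mark the 18,318 aim in SAP section 1 in the same way.
2. Protocol 9.2 and the SAP: add power or expected CI width for the primary outcome at 4,576 and over a stated range of totals, showing the mortality and the follow-up (12 or 15 months) assumed. For example, at one-year rates: 34% at 4,576, 37% at 5,000 and 54% at 8,000.
3. Protocol sections 1.7 and 2: state that the adequate-power claim and the sentence on difference or similarity apply to the full planned sample.
4. SAP 4.5: add that a non-significant primary result will be interpreted from its confidence interval and not as similarity of the two durations.
5. Minor, Protocol 9.2: give a source for 6%, or use 5.07% and report power at 16,944 both ways: about 88% for a 1-point absolute reduction and about 74% to 76% for a ratio of about 0.83.

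The cost is wording and one short table. No patients are added and no analysis changes. The stated primary power becomes less favourable.

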9.3 PROPOSED ANALYSES

For the primary outcome (all-cause mortality) we will compare time-to-event in a Cox regression model, stratifying by country and centre to account for clustering of

participants, and adjusting for cardiac history (stratification factor in randomisation). For secondary outcomes of non-cardiovascular mortality and bleeding death, we will similarly estimate cause-specific hazard ratios, censoring for competing causes of death. All analyses will be by intention-to-treat.

It is highly likely that baseline characteristics will have a major influence on the overall clinical benefits and risks [Steg et al, 2011]. We will explore efficacy and safety outcomes in the 4 pre-specified and stratified cohorts nested within the trial: (i) medically managed, (ii) percutaneous coronary intervention with bare metal stent, (iii) percutaneous coronary intervention with drug-eluting stent, and (iv) coronary artery bypass graft surgery.

In a sensitivity analysis, we will consider a two-stage individual participant data (IPD) meta-analysis where the IPD from each country are analysed separately then combined by an appropriate fixed-effect or random effects meta-analysis model [Burke et al, 2017].

The statistical methods will be documented in full in a detailed statistical analysis plan. The methods used will take into account the early stopping of the trial, and the limited numbers of events that will be available for analysis. A composite outcome of non-fatal bleeding and all-cause mortality will be explored.

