4.6 Secondary outcomes

The interpretation of trial findings for secondary outcomes will focus on the effect size and 95% CI. No formal adjustment will be made to significance levels to allow for multiplicity.

For each of the following secondary outcomes (appendix C), events are defined as the time to first outcome event during follow-up from date of the index myocardial infarction. Follow-up will be censored at competing causes of death or 15 months from date of MI, whichever occurs first.

Efficacy

- Cardiovascular death and non-fatal myocardial infarction
- Cardiovascular mortality (cardiac and non-cardiac)
- Myocardial infarction (fatal and non-fatal)
- Stent thrombosis
- Coronary revascularisation
- Thrombotic stroke

Safety

- Non-cardiovascular death (including fatal bleeding) and major non-fatal bleeding
- Non-cardiovascular death (including fatal bleeding)
- Major fatal and non-fatal bleeding
- Hospitalisation for bleeding
- Intracranial haemorrhage
- Gastrointestinal bleeding

The analysis will follow that specified for the primary outcome in section 4.5. The number and proportions of participants with an event for individual components of the secondary outcomes will also be reported alongside the composite.

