Major fatal and non-fatal bleeding	
Hospitalisation for bleeding
 
Primary or first secondary position
 
I60x, I61x, I62x, S06.4x, S06.5x, S06.6x, K92.0x, K92.1x, K 92.2x, I85.0x, I98.3x, K22.6x, K25.0x, K25.2x, K25.4x, K25.6x, K26.0x, K26.2x, K26.4x, K26.6x, K27.0x, K27.2x, K27.4x, K27.6x, K28.0x, K28.2x, K28.4x, K28.6x, K29.0x, K62.5x, K66.1x, R58x, I23.0x, I31.2x, I69.0x, I69.1x, I69.2x, H21x, H35.6x, H31.3x, H43.1x, H44.8x, H45.0x, R04.0x, R04.1x, R04.2x, R04.8x, R04.9x, T81.0x, D62x, N83.7x, N93.8x , N93.9x, O03.1x, O03.6x, O04.1x, O04.6x, O05.1x, O05.6x, O06.1x, O06.6x, O20.8x, O20.9x, O46x , O67x, O07.1x, O07.6x, O08.1x, O71.7x , O72.0x , O72.1x , O72.2x , O90.2x , P26.1x , R31x , M25.0x.
 
OR
 
Primary procedure position (OPCS4)
 
E05x , E058x , E059x , F162x , D041x , E203x , F365x , G523x , H212x , H531x , K681x , P093x , P271x , T301x , Y221x , T032x , Y221x , T032x , Y321x , V032x , A052x , A053x , A054x , A103x , A401x , A411x
 
OR
 
Death due to bleeding
 
Primary cause of death

	I60x, I61x, I62x, S06.4x, S06.5x, S06.6x, K92.0x, K92.1x, K 92.2x, I85.0x, I98.3x, K22.6x, K25.0x, K25.2x, K25.4x, K25.6x, K26.0x, K26.2x, K26.4x, K26.6x, K27.0x, K27.2x, K27.4x, K27.6x, K28.0x, K28.2x, K28.4x, K28.6x, K29.0x, K62.5x, K66.1x, R58x, I23.0x, I31.2x, I69.0x, I69.1x, I69.2x, H21x, H35.6x, H31.3x, H43.1x, H44.8x, H45.0x, R04.0x, R04.1x, R04.2x, R04.8x, R04.9x, T81.0x, D62x, N83.7x, N93.8x , N93.9x, O03.1x, O03.6x, O04.1x, O04.6x, O05.1x, O05.6x, O06.1x, O06.6x, O20.8x, O20.9x, O46x , O67x, O07.1x, O07.6x, O08.1x, O71.7x , O72.0x , O72.1x , O72.2x , O90.2x , P26.1x , R31x , M25.0x.

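### The protocol promises a cause-specific hazard ratio for bleeding death, but the SAP leaves it out without explanation and keeps only descriptive component counts

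*Protocol*

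**What the plan says.** Protocol 9.3 states: "For secondary outcomes of non-cardiovascular mortality and bleeding death, we will similarly estimate cause-specific hazard ratios", with other causes of death treated as censoring. Only these two secondary outcomes are named there. Protocol 9.2 claims that the full sample could detect "an absolute risk reduction of 0.3% (from 0.6% to 0.3%) in bleeding death, with 83% power". Protocol 7.1 also records fatal bleeding as a safety endpoint distinct from non-cardiovascular death and from major bleeding.

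Protocol Table 3 is different. Fatal bleeding appears there only inside broader safety endpoints: two built on non-cardiovascular death, and one that pools fatal with non-fatal major bleeding.

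SAP section 2 reproduces the 9.3 sentence. The outcome list in SAP 4.6 then matches the secondary endpoints of Table 3 and has no bleeding death entry. Appendix C has no row for it either, although "Death due to bleeding" is a coded block, by primary cause of death, within the major bleeding row. SAP 4.6 also undertakes to give numbers and proportions for the components of its secondary outcomes.

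**The concern.** The protocol's rationale is that longer treatment trades fewer atherothrombotic events for more bleeding, some of it fatal. Fatal bleeding is one direct route to the primary outcome, and the protocol committed to a modelled comparison of it. Under the SAP as written, a reader gets no hazard ratio and no confidence interval for that outcome.

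The SAP footnotes other departures from the protocol: the handling of the bypass and bare-metal-stent groups, centre stratification, and haemoglobin. Bleeding death has no such note, so a reader cannot tell a decision from an oversight. In an open-label trial that stopped early, an unexplained gap of this kind invites questions about selective reporting.

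**Working it through.** **1. The plan's own power figure.** Inputs from Protocol 9.2: p1 = 0.006, p2 = 0.003, n = 8,472 per group, two-sided 5%, two proportions without continuity correction ("Stata 15.1 procedure 'power two-prop' without continuity correction").

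- Mean proportion p̄ = 0.0045.
- SE under the null = √(2·p̄(1−p̄)/n) = √(2 × 0.0045 × 0.9955 / 8,472) = 0.001028.
- SE under the alternative = √((p1(1−p1) + p2(1−p2))/n) = √((0.005964 + 0.002991) / 8,472) = 0.001028.
- Power = Φ((0.003 − 1.96 × 0.001028) / 0.001028) = Φ(0.958) = 83.1%.

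The stated 83% reproduces.

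**2. The same effect at the recruited UK number.** 4,576 patients at 1:1 gives 2,288 per arm.

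- Expected deaths: 2,288 × 0.006 = 13.7 and 2,288 × 0.003 = 6.9, about 21 in total.
- Power = Φ((0.003 − 1.96 × 0.001979) / 0.001978) = Φ(−0.444) = 33%. Schoenfeld's event-based formula gives 35%.
- SE of the log hazard ratio ≈ √(1/13.7 + 1/6.9) = 0.467. Around a hazard ratio of 0.5, the 95% CI is 0.5 × exp(±1.96 × 0.467) = 0.20 to 1.25.

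Restricting to 92.5% of UK patients (4,233), the basis of the original power statement, gives 12.7 against 6.3 deaths, 31% power and an interval of 0.19 to 1.30. The number of New Zealand patients is not stated. If, purely as an assumption, they doubled the total to 4,576 per arm, power would be about Φ(2.918 × √(4,576/8,472) − 1.96) = Φ(0.184) = 57%, where 2.918 = 0.003/0.001028 before rounding.

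**3. Does another listed outcome supply the estimate?** From SAP Appendix C:

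| Outcome | Cause-of-death codes | Hazard ratio for fatal bleeding? |
|---|---|---|
| Non-cardiovascular death | Other chapter letters, no I codes | No: omits I60–I62, I85.0, I98.3, I23.0, I31.2, I69.0–I69.2 and adds all other non-cardiovascular deaths |
| Cardiovascular death | All I codes | No: takes in the deaths just listed, as an efficacy outcome |
| Major fatal and non-fatal bleeding | Full bleeding list, plus bleeding admissions and procedures | No: deaths are pooled with admissions |
| Intracranial and gastrointestinal bleeding | Site-specific bleeding codes | No: deaths are pooled with events, one site each |

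The label of the first row says that fatal bleeding is included, but its codes capture only fatal bleeds outside chapter I.

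**4. What remains.** SAP 4.6 promises component counts and follows the 4.5 template, which summarises events by treatment group. Fatal bleeding by arm should therefore appear descriptively. Two details are open. The component sentence does not itself say that counts are by arm. Also, because outcomes are defined as time to first event, it is not stated whether a fatal bleed after an earlier bleeding admission counts in the fatal component.

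**The case against.** A reader might infer that nothing comparing fatal bleeding between the arms will be reported. The documents do not support that. Component counts and proportions are promised, the fatal block is separately coded, and the template summarises by arm. What is lost is the modelled estimate and its interval.

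A reader might also infer that the SAP struck out a listed endpoint. It did not: Table 3 never listed bleeding death separately, and SAP 4.6 is faithful to Table 3. The inconsistency begins inside the protocol, between Table 3 and section 9.3. That stands as mitigation. But SAP section 2 carries the 9.3 commitment forward, so the SAP is also inconsistent with itself.

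Protocol 9.3 further allows methods to reflect early stopping and few events. That could justify the omission, but the SAP does not invoke it for this outcome. It does invoke early stopping to explain dropping centre from the primary model.

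Feasibility is a fair point. Treatment plus five terms for a six-level cardiac history factor makes six parameters, or about 20.6/6 = 3.4 events each. Stratifying by centre as well would be worse. This limits the form of the model, not the case for an estimate.

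Finally, fatal bleeding is not the whole rationale. Protocol 1.2 lists several other links between bleeding and mortality, and on the plan's figures bleeding death would account for 0.3 of the 1.69 percentage-point mortality difference, about 18%. Major bleeding and non-cardiovascular death are both modelled. This keeps the matter at the level of a secondary outcome.

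**Conclusion.** The point holds as an unexplained omission of a protocol-specified analysis. The SAP provides no hazard ratio or interval for bleeding death, no listed outcome supplies one, and no reason is given. Descriptive counts remain. The primary analysis is unaffected.

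Low power is not a reason to withhold the estimate, since SAP 4.6 bases interpretation of secondary outcomes on effect size and 95% CI. The expected precision (about 21 UK deaths, 33% power, interval roughly 0.20 to 1.25 around 0.5) assumes that the plan's rates apply. Those rates derive from one-year data, whereas follow-up runs to 15 months. The figures also leave out New Zealand patients and ignore the exclusions from the analysis population in SAP 4.1.

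**What to change.** - Add bleeding death to the safety list in SAP 4.6, with its own Appendix C row reusing the existing primary-cause bleeding codes.
- Estimate a cause-specific hazard ratio with 95% CI from a Cox model stratified by country. Add cardiac history only if events allow, and do not stratify by centre. Footnote these departures from Protocol 9.3.
- Report counts and proportions by treatment group, and state that fatal bleeds following an earlier bleeding admission are included.
- Present the result as an imprecise estimate.
- Note in the SAP that Table 3 and section 9.3 of the protocol differ on this outcome.

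If the sponsor decides against modelling, the minimum is a footnote giving the reason and explicit by-arm wording for the component counts.

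The cost is small: one list entry, one appendix row, a footnote and one more model run. The code list and the data sources are already specified. The I-chapter mismatch in the non-cardiovascular death outcome is a separate matter that this change does not resolve.
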